16.1.1 Plasma Pharmacokinetic Parameters

The following plasma PK parameters for RO7017773 and metabolites will be estimated.

Parameter	Description
Tmax	Time to maximum plasma concentration. First observed time to reach peak analyte concentration obtained directly from the experimental data without interpolation, expressed in time units.
Cmax	Maximum plasma concentration. Observed peak analyte concentration obtained directly from the experimental data without interpolation, expressed in concentration units
AUC0-t	Area under the plasma concentration-time curve from time 0 to t hours post-dose.
AUClast	Area under the plasma concentration-time curve (time 0 to time of last quantifiable concentration).
AUCinf	Area under the plasma concentration-time curve (time 0 to infinity). Percent extrapolation less than or equal to 20% is required to obtain a reliable AUCinf.
T1/2	Apparent terminal half-life, calculated as $\ln(2)/\lambda z$
CL/F	Apparent oral clearance, calculated as Dose/AUCinf

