ALL PARTS	
 
• To screen for the presence of RO7017773-derived metabolites.
 
• To assess the relative abundance and PK parameters of any metabolite as appropriate
 
	
 
• PK concentrations of RO7017773-derived metabolites, if appropriate.
 
• PK concentrations of RO7017773-derived metabolites, if appropriate.
 

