##### **9.4.3.1 Pharmacokinetic Parameters**

The primary RO7017773 PK study variable will be the AUC (AUC0-inf if it can be derived, otherwise truncated as appropriate) and Cmax. For Treatment C of Part 1, Tmax is additionally considered as primary PK variable. All other PK parameters will be regarded as secondary.

The following PK parameters of RO7017773 will be read from the concentration versus time profiles or estimated using non-compartmental methods where appropriate:

- Tmax : Time to maximum plasma concentration
- Cmax : maximum observed plasma concentration
- AUC0-t : area under the plasma concentration-time curve up to time t
- AUC0-last : area under the plasma concentration-time curve up to the last measurable concentration

- $AUC_{0-\infty}$ : area under the plasma concentration-time curve extrapolated to infinity
- $T_{1/2}$  : apparent terminal half-life, computed as  $\ln(2)/\lambda_z$
- $CL/F$ : apparent oral clearance, calculated as Dose/ $AUC_{0-\infty}$

Additional PK parameters may be reported as appropriate.

All pharmacokinetic concentration and calculated PK parameters for RO7017773 will be presented in individual listings and summary tables (including descriptive summary statistics: mean, standard deviation, coefficient of variation, median, minimum, and maximum), and graphs (including concentration vs. time plots on linear and semi-logarithmic scales) as appropriate.

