5.3 Exploratory

- To screen for the presence of RO7017773-derived metabolites.
- To assess the relative abundance and PK parameters of any metabolite as appropriate

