5.3.1 Exploratory Endpoints

- Concentrations of RO7017773-derived metabolites, if appropriate

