16.0 Pharmacokinetic Analyses

16.1 Pharmacokinetic Variables

The reporting of pharmacokinetic concentrations and calculation of pharmacokinetic parameters will be in accordance with Roche clinical pharmacology guiding principles for calculation and analyses of non-compartmental pharmacokinetic parameters version 4.

Individual plasma concentrations of RO7017773 and metabolites (if appropriate) will be presented together with descriptive statistics by treatment.

Individual plasma PK parameters of RO7017773 and metabolites (if appropriate) will be estimated using non-compartmental methods with WinNonlin® for each subject by treatment.

Individual values of calculated PK parameters will be presented together with their descriptive statistics by treatment. The following descriptive statistics will be used: number of subjects, mean, geometric mean, SD, CV, geoCV, median, min, and max. For t_{max}, only median, min and max will be presented.

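### SAP 16.1.1 lists CL/F, calculated as Dose/AUCinf, for metabolites as well as RO7017773, but only RO7017773 is dosed; the row should be limited to the parent

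*SAP*

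**What the plan says.** SAP 16.1.1 gives a single table of seven parameters (Tmax, Cmax, AUC0-t, AUClast, AUCinf, T1/2, CL/F), introduced by "The following plasma PK parameters for RO7017773 and metabolites will be estimated". The CL/F row reads "Apparent oral clearance, calculated as Dose/AUCinf". No row is limited to one analyte.

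SAP 16.1 makes the metabolite work conditional: "Individual plasma PK parameters of RO7017773 and metabolites (if appropriate) will be estimated using non-compartmental methods with WinNonlin® for each subject by treatment". It also ties the calculations to the "Roche clinical pharmacology guiding principles for calculation and analyses of non-compartmental pharmacokinetic parameters version 4", which is not among the documents.

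The Protocol's list in 9.4.3.1 also contains CL/F, but it is headed "The following PK parameters of RO7017773 will be read from the concentration versus time profiles", so it covers the parent. It leaves room for further unnamed parameters. Protocol 8.5 foresees parameters for a metabolite, as appropriate, without naming any.

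SAP 5.3 carries the exploratory objective "To assess the relative abundance and PK parameters of any metabolite as appropriate". The matching endpoint is "Concentrations of RO7017773-derived metabolites, if appropriate" in SAP 5.3.1, and "PK concentrations of RO7017773-derived metabolites, if appropriate" in Protocol Table 6.

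**The concern.** CL/F is meaningful when the numerator is the dose of the substance whose AUC is in the denominator. That is true of RO7017773. It is not true of a metabolite, because no metabolite is given and the amount formed is not known from plasma samples after an oral dose of parent. If metabolites are quantified and the table is followed as written, the report would show an apparent oral clearance for each metabolite that does not measure clearance. A reader could take it at face value, for example when comparing how quickly parent and metabolite are eliminated.

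The same table has no parameter relating metabolite to parent, although relative abundance is a stated exploratory objective.

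**Working it through.** The documents state no figure to reproduce, since this is a question of definition. The check is a mass balance under linear kinetics in molar units. The symbols are: F, bioavailability of the parent; fa, fraction of the dose absorbed; fm, fraction of parent converted to the metabolite; CL and CLm, clearances of parent and metabolite. The documents give none of these, so every value below is assumed for illustration.

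**Parent.** AUCinf = F × Dose / CL, so Dose / AUCinf = CL/F. The SAP's definition is correct for RO7017773.

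**Metabolite, case 1: formed only from parent already in the circulation.**
- AUCinf,m = fm × F × Dose / CLm, so Dose / AUCinf,m = CLm / (fm × F).
- Relative to CLm/F this is a factor of 1/fm.
- With fm = 0.5 the factor is 1/0.5 = 2; with fm = 0.1 it is 1/0.1 = 10; only at fm = 1 is it 1.
- Numerical integration of a one-compartment parent-to-metabolite model agrees. With Dose = 1, CL = 1, CLm = 2, F = 1 and fm = 0.5, Dose/AUCinf,m is 4.0 against CLm/F = 2.0. With F = 0.5 and fm = 0.1 it is 40.0 against CLm/F = 2/0.5 = 4.0.

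**Metabolite, case 2: first-pass loss yields the same metabolite fraction.**
- AUCinf,m = fa × fm × Dose / CLm, so Dose / AUCinf,m = CLm / (fa × fm).
- Relative to CLm/F the factor is F / (fa × fm).
- With F/fa = 0.4 and fm = 0.5 it is 0.4/0.5 = 0.8, which is an understatement.

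**Units.** If dose and AUC are in mass units, the quotient carries a further factor, the molecular weight of the parent divided by that of the metabolite.

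In both cases the quotient contains fm, which these samples cannot identify. The same fm = 0.5 gives 2 in case 1 and 0.8 in case 2, so even the direction of the error depends on where the metabolite is formed.

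**Relative abundance.** The planned outputs include concentrations by treatment (SAP 16.1) and Cmax and AUC for both analytes (SAP 16.1.1). A metabolite-to-parent AUC ratio can be built from these after molar adjustment. In case 1 it equals fm × CL / CLm; with fm = 0.5, CL = 1 and CLm = 2 it is 0.25. It describes relative exposure and makes no claim to be a clearance.

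**Reach.** The models in SAP 16.1.1.1 and 16.1.1.2 are specified for RO7017773 Cmax and AUC. CL/F does not enter them.

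**The case against.** The strongest reply is that the error may never reach a table. Metabolite parameters are estimated only if judged appropriate, and the sponsor's guiding principles govern the calculations and may already confine CL/F to the parent or define a ratio. The sponsor, not the contract organisation, supplies the PK parameter outputs (SAP 7.3 and 9.5). This stands as a limit on likelihood, and it means nobody can say that wrong clearances will be reported. It does not cure the text. The condition decides whether metabolite parameters are estimated, not which rows then apply. The guiding principles cannot be consulted here. SAP 3.0 says that the plan covers the sponsor's PK results too.

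Three stronger readings are tempting, and the documents do not support them:

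- A reader might infer a definite overstatement of 1/fm, such as 2-fold or 10-fold. That holds only if the metabolite forms solely from circulating parent, and no value of fm is given. Case 2 above reverses the direction.
- A reader might infer an undeclared departure from the Protocol, because SAP 7.1 reports none. Protocol 8.5 and the exploratory objective in Protocol Table 6 already foresee metabolite parameters. Only the extension of the CL/F row goes beyond Protocol 9.4.3.1.
- A reader might infer that relative abundance has no planned data behind it. Its mapped endpoint is metabolite concentrations, which are planned, as are Cmax and AUC for both analytes, and Protocol 9.4.3.1 permits additional parameters. The absence of a named ratio is missing detail, not an error.

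**Conclusion.** As written, SAP 16.1.1 assigns metabolites a CL/F that is not an apparent oral clearance. This follows from the definition and from the fact that only the parent is dosed, and does not depend on any assumed value. The numerical size and direction of the error cannot be determined from the documents; the factors of 2, 10 and 0.8 are illustrations under stated assumptions.

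The consequence is small. It is confined to conditional, exploratory metabolite outputs, and no RO7017773 comparison in Part 1 or Part 2 changes. A correction is still worth making because the row is wrong as it stands and nearly free to put right. The missing ratio is a suggestion only.

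**What to change.** In SAP 16.1.1, mark the CL/F row as applying to RO7017773 only. Keep Tmax, Cmax, AUC0-t, AUClast and, where derivable, AUCinf and T1/2 for metabolites. If the guiding principles already restrict CL/F to the parent, this simply brings the table into line. The cost is a few words.

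Optionally, add that if metabolites are quantified, metabolite-to-parent ratios of AUC and Cmax will be reported by treatment, molar-adjusted where possible. This needs no new samples, but it does need molecular weights. Protocol 4.2.2 allows screening with non-validated methods and retrospective measurement in residual samples, so the SAP should also say that a ratio without a reference standard would be labelled semi-quantitative.

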16.1.1.1 Part 1 Bioavailability and Food Effect

The bioavailability of RO7017773 administered as a Phase I capsule compared to a Phase II tablet, the bioavailability of RO7017773 administered as a Phase II tablet dispersed in water compared to a Phase II tablet swallowed whole, and the effect of a high-fat, high calorie meal on the bioavailability of RO7017773 administered as Phase II tablet, will be assessed.

90% confidence intervals (CIs) of the geometric least-squares (LS) mean ratios of the RO7017773 plasma PK parameters Cmax and AUCinf will be calculated. If AUCinf cannot be derived, Cmax and AUClast will be used. The following linear mixed effects model will be implemented using the natural log-transformed parameters, where τ_i are fixed effects for treatment ($i=1, \dots, 4$), π_k are fixed effects for period ($k=1, \dots, 4$), ω_j are fixed effects for sequence ($j=1, \dots, 4$), and s_m is the random effect for subject m . The random subject effects and the random errors ϵ_{ijkm} are assumed to be independent and normally distributed with zero means and standard deviations σ_s and σ_ϵ , respectively.

$$Y_{ijkm} = \mu + \tau_i + \pi_k + \omega_j + s_m + \epsilon_{ijkm}$$

Estimates on the original scale of measurement will be obtained by exponentiating point estimates on the natural log scale. Geometric LS means will be provided for each treatment. In all comparisons, treatment B will be used as the reference. No adjustments will be made for multiplicity.

The following SAS PROC MIXED pseudo-code may be used:

```
proc mixed data = adpp;
  by analyte parameter;
  class treatment period sequence subject;
  model ln(aval) = treatment period sequence/ddfm=kr;
  random subject;
  lsmeans treatment / alpha = 0.1;
  estimate "A vs B (capsule vs tablet)" treatment 1 -1 0 0 /e cl alpha=0.1;
  estimate "C vs B (fed vs fasted)" treatment 0 -1 1 0 /e cl alpha=0.1;
  estimate "D vs B (dispersed in water vs swallowed)" treatment 0 -1 0 1 /e
  cl alpha=0.1;
```

run;

16.1.1.2 Part 2 Bioavailability

The bioavailability of RO7017773 administered as a Phase II tablet containing flavor and/or sweetener dispersed in water compared to a Phase II tablet without flavor and/or sweetener dispersed in apple juice will be assessed.

90% CIs of the geometric LS mean ratios of the RO7017773 plasma PK parameters Cmax and AUCinf will be calculated. If AUCinf cannot be derived, Cmax and AUClast will be used. The following linear mixed effects model will be implemented using the natural log-transformed parameters, where τ_i are fixed effects for treatment ($i=1, \dots, 4$), π_k are fixed effects for period ($k=1,2$), and s_m is the random effect for subject m . The random subject effects and the random errors ϵ_{ijkm} are assumed to be independent and normally distributed with zero means and standard deviations σ_s and σ_ϵ , respectively.

$$Y_{ijkm} = \mu + \tau_i + \pi_k + s_m + \epsilon_{ijkm}$$

Estimates on the original scale of measurement will be obtained by exponentiating point estimates on the natural log scale. Geometric LS means will be provided for each treatment. Treatment B will be used as the reference. No adjustments will be made for multiplicity.

The following SAS PROC MIXED pseudo-code may be used:

```
proc mixed data = adpp;
  by analyte parameter;
  class treatment period subject;
  model ln(aval) = treatment period /ddfm=kr;
  random subject;
  lsmeans treatment / alpha = 0.1;
  estimate "A vs B" treatment 1 -1 /e cl alpha=0.1;
run;
```

17.0 Safety Analyses

17.1 Safety Variables

- Adverse Events (AEs)
- Clinical Laboratory Evaluations
 - Clinical Chemistry
 - Hematology
 - Urinalysis
 - Coagulation
- Vital Signs
 - Supine Blood Pressure
 - Systolic Blood Pressure
 - Diastolic Blood Pressure
 - Pulse rate
 - Oral body temperature
- Electrocardiograms (ECG)
 - Heart Rate
 - PR Interval
 - QRS-Duration
 - QT Interval
 - RR Interval
 - QTc (Frederica) Interval

- Physical Examination

17.1.1 Adverse Events

Treatment emergence will be evaluated for all AEs. Treatment-emergent adverse events (TEAE) are those which occur after the first dose of study drug.

TEAEs occurring following dosing in a specific period but before dosing in the next period will be attributed to the treatment in that period. If the time is missing for an AE on a dosing day then the AE will be attributed to the treatment given on that day.

The following missing data will be imputed as defined (for calculations only / will not be presented):

- Missing AE start and / or end times for the calculation of onset and duration will be assumed to be at 00:01 for a start time and 23:59 for end times
- Missing AE severity or relationship will be assumed to be severe or related, respectively
- Missing AE start times for the determination of treatment emergence will be assumed to occur after treatment unless partial date documents the AE as happening prior to treatment
- Missing AE start times for the determination of treatment assignment will be assumed to occur after treatment on the recorded date one minute after dosing
- Missing AE start date will be assumed to be after treatment for the determination of TEAE but will not be attributed to a specific treatment

A summary of number and percentage of subjects reporting TEAEs, TEAEs by severity and relationship, serious AEs (SAEs), and subjects who discontinued study drug due to an AE will be provided.

A summary of the number and percentage of subjects reporting each TEAE, categorized by system organ class and preferred term coded according to the Medical Dictionary for Regulatory Activities (MedDRA), will be presented by treatment and overall. Counting will be done by subject only, not by event; subjects will only be counted once within each body system or preferred term.

A summary of the number and percentage of subjects reporting each TEAE will be presented by relationship to study drugs (as recorded on the eCRF) and by treatment and overall. Subjects with multiple events within a system organ class or preferred term will be counted under the category of their most drug-related event within that system organ class or preferred term.

A summary of the number and percentage of subjects reporting each TEAE will be presented by severity (as recorded on eCRF) and by treatment and overall. Subjects with multiple events within a system organ class or preferred term will be counted under the category of their most severe event within that system organ class or preferred term.

All AEs (including non-treatment-emergent events) recorded on the eCRF will be listed by subject.

A separate listing of AEs leading to study drug discontinuation will be provided.

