**Table 6 Objectives and Endpoints**

	Objectives	Endpoints
Primary		
PART 1	
 
• To assess the relative bioavailability of Phase II tablet formulation compared to Phase I capsule formulation of RO7017773 swallowed whole under fasting conditions following single oral dose administration.
 
	
 
• RO7017773 concentrations and RO7017773 pharmacokinetics (PK) parameters
 

PART 2	
 
• To assess the taste masking of RO7017773 Phase II tablet formulation containing sweetener and flavor dispersed in water and the RO7017773 Phase II tablet formulation without sweetener and flavor dispersed in apple juice.
 
	
 
• Taste questionnaire
 

Secondary		
PART 1	
 
• To assess the PK of RO7017773 Phase II tablet formulation dispersed in water or swallowed whole.
 
• To assess the effect of a high-fat meal on the PK (PK) of a single oral dose of RO7017773 Phase II tablet formulation.
 
• To assess the taste of RO7017773 Phase II tablet formulation without sweetener and flavor dispersed in water.
 
	
 
• RO7017773 concentrations and RO7017773 PK parameters
 
• RO7017773 concentrations and RO7017773 PK parameters
 
• Taste questionnaire
 

PART 2	
 
• To assess the PK of RO7017773 Phase II tablet formulation containing sweetener and flavor dispersed in water and the RO7017773 Phase II tablet formulation without sweetener and flavor dispersed in apple juice.
 
	
 
• RO7017773 concentrations and RO7017773 PK parameters
 

ALL PARTS	
 
• To evaluate the safety and tolerability of single oral doses of different RO7017773 formulations in healthy participants.
 
	
 
• Incidence and severity of AEs.
 
• Changes in vital signs, physical findings, ECG parameters, and clinical laboratory results during and following RO7017773 administration
 

Tertiary/Exploratory		

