### **8.3.1 Time Period and Frequency for Collecting Adverse Event and Serious Adverse Event Information**

The method of recording, evaluating, and assessing causality of AEs and SAEs and the procedures for completing and transmitting SAE reports are provided in [Appendix 2](#).

Investigators will seek information on adverse events at each participant's contact. All adverse events, whether reported by the participant or noted by study personnel, will be recorded in the participant's medical record and on the Adverse Event eCRF as follows:

**After informed consent** has been obtained **but prior to initiation of study treatment**, only serious adverse events caused by a protocol-mandated intervention should be

reported (e.g., serious adverse events related to invasive procedures such as biopsies). Any other adverse event should not be reported.

**After initiation of study treatment**, all adverse events, regardless of relationship to study treatment, will be reported until the follow-up visit (approximately 7 to 14 days after the last dosing).

**Post-study adverse events and serious adverse events:** The Investigator is not required to actively monitor participants for adverse events after the end of the adverse event reporting period (after the follow-up visit approximately 7 to 14 days after the last dosing).

However, if the Investigator learns of any SAE (including a death) or other adverse events of concern that are believed to be related to prior treatment with study treatment, at any time after a participant has been discharged from the study, and the Investigator considers the event to be reasonably related to the study treatment or study participation, the Investigator must promptly notify the Sponsor. For the procedure of reporting, see [Appendix 2](#).

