### **8.3.3        Follow-Up of Adverse Events and Serious Adverse Events**

#### **8.3.3.1      Investigator Follow-Up**

The Investigator should follow each adverse event until the event has resolved to baseline grade or better, the event is assessed as stable by the Investigator, the event is otherwise explained, the participant is lost to follow-up ([Section 7.3](#)), or the participant withdraws consent. Every effort should be made to follow all serious adverse events considered to be related to study treatment or trial-related procedures until a final outcome can be reported.

During the study period, resolution of adverse events (with dates) should be documented on the Adverse Event eCRF and in the participant's medical record to facilitate source data verification. If, after follow-up, return to baseline status or stabilization cannot be established, an explanation should be recorded on the Adverse Event eCRF.

All pregnancies reported during the study should be followed until pregnancy outcome and reported according to the instructions provided in [Section 8.3.5](#).

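### An adverse event with no start date is put in no treatment column, even when its other recorded dates leave only one possible treatment

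*SAP*

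**What the plan says.** SAP 17.1.1 (Adverse Events) first gives a general attribution rule: "TEAEs occurring following dosing in a specific period but before dosing in the next period will be attributed to the treatment in that period". A list of conventions for missing data follows, and its last item reads: "Missing AE start date will be assumed to be after treatment for the determination of TEAE but will not be attributed" to any one treatment. No exception is attached for an end date, a partial start date or the contact at which the event was first reported. The list does mention partial dates once ("unless partial date documents the AE as happening prior to treatment"), but that clause decides treatment emergence and not treatment assignment.

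The summaries of treatment-emergent events by system organ class and preferred term "will be presented by treatment and overall"; those by relationship and severity use the same columns. Participants are counted once per row, and under SAP 9.1.4 the denominator is the number exposed to the treatment.

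On data collection, Protocol 8.3.1 says "Investigators will seek information on adverse events at each participant's contact", and Protocol 8.3.3.1 says that during the study "resolution of adverse events (with dates) should be documented on the Adverse Event eCRF". The safety objective in Protocol Table 6 is "To evaluate the safety and tolerability of single oral doses of different RO7017773 formulations in healthy participants".

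**The concern.** The safety objective concerns the different formulations, and only the treatment columns speak to it. The last item in the list takes an event that the SAP itself accepts as treatment-emergent and withholds it from every one of those columns, whether or not the treatment can be known. Where the treatment is known, this conflicts with the general rule in the same section, which assigns an event to the period in which it occurred.

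The error has one possible direction. The denominator is fixed by exposure, so the rule can lower a treatment's numerator or leave it alone, but cannot raise it. With 16 and 8 participants, one lost participant is visible in a percentage.

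**Working it through.** The documents state no AE rate, no missing-date rate and no sample size based on safety, so there is no planned figure to reproduce. The check is a logical one, followed by the size per participant.

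**1. Is the treatment ever determined without a start date?** Take an AE with no start date and a recorded end date before the Period 2 dose.
- Lower bound on onset: the SAP deems the event to be after the first dose. Protocol 8.3.1 supports this, because before first dosing only serious events caused by a protocol-mandated intervention are reported.
- Upper bound on onset: the end date, which is before the Period 2 dose.
- Onset therefore lies between the Period 1 and Period 2 doses. The general rule would assign the Period 1 treatment; the last item in the list assigns none.

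**2. How far does this extend to later periods?** An end date in Period 3 alone is compatible with onset in Period 1, 2 or 3, so it does not fix the treatment. A month-only start date is also weak: four doses 7 to 10 days apart span 3 × 7 = 21 to 3 × 10 = 30 days, so one month can cover several or all Part 1 periods. The contact of first report, taken with the preceding AE inquiry, could bracket onset. Protocol 4.1 has participants in-house from Day -1 to Day 3, with visits on Days 4 and 5. But the documents do not say that the eCRF holds a report date.

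**3. Size per affected participant**, if no other event already counts that participant in the row. Effect = 1/n, with n the number exposed to the treatment (SAP 6.0):
- Part 1, n = 16: 1/16 = 6.25 points.
- Part 1 if only 12 were exposed to a treatment (assumption, borrowing the minimum evaluable number): 1/12 = 8.33 points.
- Part 2, n = 8: 1/8 = 12.5 points.

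**4. Expected size.** Let p be the true incidence under a treatment and q the share of participant-level events with a missing start date (both assumed). Expected reported incidence = p(1 − q), so the shift is −pq.

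| p | q = 0 | q = 1% | q = 5% | q = 10% |
|---|---|---|---|---|
| 10% | 0 | −0.10 | −0.50 | −1.00 |
| 25% | 0 | −0.25 | −1.25 | −2.50 |
| 50% | 0 | −0.50 | −2.50 | −5.00 |

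(percentage points)

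Only the events whose period can be determined are recoverable. At p = 25% and q = 5%, the SAP rule gives 23.75%. If half the undated events can be placed, the figure is 0.25 × (1 − 0.05 × 0.5) = 24.4%; if all can, 25%.

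**5. Chance that the issue arises at all.** For 20 AEs, P(at least one missing date) = 1 − (1 − q)^20, which is 18% at q = 1% and 64% at q = 5% (assumed rates).

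**The case against.** The best defence is that the rule declines to guess. SAP 9.1.2 makes no imputation the default, and the safety comparison is descriptive, with no hypothesis tests (SAP 9.4.3). Missing start dates should be rare given the in-house stay, the questioning at each contact and the querying of problem values (SAP 8.2). The event also remains in the overall column and in the by-subject listing, where it is easy to see among 16 or 8 participants. The table shells are a separate document, so an unattributed column or a footnote cannot be excluded. Most of this stands, and it limits the weight of the point. It does not answer the case in step 1, where placing the event needs no guess.

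A reader might infer three stronger things that the documents do not support:
- *That by-treatment incidence is biased low in this trial.* That holds only if a start date is actually missing, and no rate is given.
- *That the rule is why the treatment columns do not reconcile with overall.* Participants are counted once per row in a crossover. Someone with the same term under two treatments counts once in each column and once overall, so the columns need not sum even with complete dates.
- *That the treatment of an undated event can usually be recovered.* After Period 1 an end date is only an upper bound, and a recorded date of first report is not documented.

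The contrast with neighbouring conventions should also not be pressed far. Missing severity and relationship are set to the worst case, but the rule for a missing time on a dosing day has no such direction. The missing-date rule is itself cautious about emergence, and it favours no particular formulation by design.

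**Conclusion.** The point holds as a minor, conditional one. SAP 17.1.1 withholds attribution even where recorded dates leave a single possible treatment, and nothing else in the SAP or protocol text restores it. If such an event occurs, the affected column is too low by up to 6.25 points (Part 1, 16 exposed) or 12.5 points (Part 2, 8 exposed) per participant not otherwise counted in the row. Overall incidence and the listings are unaffected. Under the assumed ranges (p from 10% to 50%, q from 1% to 10%) the expected shift runs from −0.1 to −5.0 points if every undated event could be placed; it is smaller if only some can, and zero if no date is missing. The case for changing the rule rests on its conflict with the section's own general rule and on the low cost, not on a large expected effect.

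**What to change.** Before database lock, replace the last item of the missing-data list in SAP 17.1.1 with:

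> An AE with a missing or partial start date is treatment-emergent unless the available date information places it before first dose. If the recorded information (partial start date, end date and, where recorded, the contact of first report together with the preceding AE inquiry) is compatible with onset in only one treatment period, the AE is attributed to that period's treatment; otherwise it is shown under overall only, with a footnote giving the number of unattributed TEAEs.

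The condition of a single possible period matters. A convention that always chose the most recent treatment before the earliest known bound would push ambiguous later-period and month-only cases onto the latest possible treatment.

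The cost is one changed item in the SAP, a few lines in the ADAE derivation and a table footnote. Where first report is used, a late report could still misplace an event, because the bracket assumes that the participant would have mentioned it at the preceding inquiry.
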